## Pharmacokinetic (PK) Population

The PK Population will include all randomized patients receiving any ocrelizumab treatment who had at least one measurable concentration value unless major protocol deviations or unavailability of information occurred that may interfere with the PK evaluation.

## 4.2 ANALYSIS OF STUDY CONDUCT

All relevant data up to the point of the CCOD will be included to evaluate substudy conduct. The following summaries will be prepared to evaluate the substudy conduct (number of patients and percentage):

• List of randomization failures – these are patients who consented to participate in the substudy but were not randomized. A listing of these patients will be provided, which will include whether the patient was already or newly enrolled,

date of first ocrelizumab treatment, date of informed consent and the reason for non-randomization.

- Enrollment by country and center. A summary of randomized treatment assignments will be presented. A summary of the numbers of patients enrolled but not randomized will also be presented.
- Randomization assignment by stratification factors: region (US, Canada, Australia versus ROW) and 1st Randomized Dose. Listings will be prepared to show a) these stratification factors and b) any discrepancies in these stratification factors when the clinical trial database and IxRS databases are compared.
- Summaries of patient disposition (tabular and graphical), including the number of randomized doses received and numbers of patients ongoing in and discontinued from the substudy. This will be presented for all patients, for patients already enrolled in the main study, and for patients newly enrolled.
- Summary of reasons for early discontinuation from the substudy, for all patients, for patients already enrolled in the main study, and for patients newly enrolled.
- Summary of reasons for early discontinuation from ocrelizumab treatment, for all patients, for patients already enrolled in the main study, and for patients newly enrolled.
- Summary of reasons for early discontinuation from the main study, for all patients, for patients already enrolled in the main study, and for patients newly enrolled.
- Summaries of ITT, PP, Safety and PK Populations, showing numbers of patients in each population
- Summary and listing of major protocol deviations, leading to exclusion from the PP Population.

## 4.3 ANALYSIS OF TREATMENT GROUP COMPARABILITY

To assess treatment group comparability, summaries of baseline characteristics will be presented by randomized treatment group. These will be for the ITT Population only.

For continuous variables, the mean, median, SD, minimum, and maximum will be calculated. For categorical variables, the number and percentage in each category will be displayed. The units/categories to be used are indicated within the brackets and separated by commas.

# 4.3.1 Demography

In addition to summary statistics and frequency counts for all patients in the ITT Population, demographic characteristics will also be summarized separately for patients already enrolled in the main study, and for patients newly enrolled. The following characteristics will be summarized:

- Age at Randomization (years): summary statistics displayed will include mean, median, SD, minimum, and maximum, percentage and number in each category (<40, ≥40). Note that the main study required patients to be aged 18-55 inclusive, but there are no specific age requirements for the substudy.
- Sex at Screening Visit of Main Study: the number and percentage of male and female patients will be displayed.
- Race at Screening Visit of Main Study: the number and percentage of the following categories will be displayed: White; Black or African American; Asian (Indian Subcontinent, Other than Indian subcontinent), American Indian or Alaska Native; Native Hawaiian or other Pacific Islander; Multiple and Unknown
- Ethnicity at Screening Visit of Main Study: the number and percentage of the following categories will be displayed: Hispanic or Latino, not Hispanic or Latino, Not Reported and Unknown
- Weight (kg) at Screening Visit of Main Study: summary statistics will be displayed, as described for age at randomization.
- Body Mass Index (BMI) at Screening Visit of Main Study: summary statistics will be displayed, as described for age at randomization.
- Details of demographic characteristics will be listed.

## 4.3.2 MS Disease History at Randomization

- Duration since MS symptom onset at randomization (years): summary statistics calculated will include mean, median, SD, minimum, and maximum (calculated in years, i.e., divide by 365.25). Frequency counts will also be presented.
- Duration since MS diagnosis at randomization (years): summary statistics calculated will include mean, median, SD, minimum and maximum (calculated in years, i.e., divide by 365.25). Frequency counts will also be presented.

Duration since MS symptom/diagnosis onset will be calculated up to the randomization date. If month of symptom/diagnosis onset date is missing, the month of January will be used. If symptom/diagnosis onset date is missing, the first (1st) of the month will be used.

Details of MS disease history will be listed.

## 4.3.3 Pre-Randomization IRRs and Serious IRRs

The number of patients with an ocrelizumab infusion, the number and percentage with any pre-randomization IRR and the number and percentage with any pre-randomization

serious IRR will be presented. For newly enrolled patients randomized at Dose 2, these numbers will be presented at Dose 1 Infusion 1, Dose 1 Infusion 2 and overall. For previously enrolled patients randomized at Dose 3, 4 or 5, these numbers will be presented at Dose 1 Infusion 1, Dose 1 Infusion 2, Dose 2, Dose 3, Dose 4 and overall. An overall summary of these numbers for all patients in the ITT Population will also be presented.

## 4.3.4 Previous Diseases (Other Than MS) Prior to Randomization

Diseases reported on the "General Medical History and Baseline Conditions Log" eCRF page are summarized as previous diseases if disease status was recorded as a) "Resolved" or as b) "Ongoing" (with or without treatment) and disease end date was known to be before date of substudy randomization or if c) the "End Date Unknown" box was checked (which indicates the disease had ended but the end date was unknown).

Diseases reported on the "Adverse Event/IRR/MS Relapse" eCRF page are summarized as previous diseases if a) AE onset date was on or after date of first ocrelizumab treatment in the main study, and AE end date was before the date of substudy randomization or b) if AE onset date was before date of first ocrelizumab treatment in the main study, and AE intensity worsened after initiation of ocrelizumab treatment but before date of substudy randomization, and AE end date was before the date of substudy randomization.

Previous diseases reported via the "General Medical History and Baseline Conditions Log" eCRF are summarized separately from those reported via the "Adverse Event/IRR/MS Relapse" eCRF page. In each of these two separate summaries, the total number of patients with at least one previous disease and the total number of previous diseases will be presented. The number and percentage of patients reporting previous diseases will be presented by system organ class (SOC) and preferred term (PT) (for further details of how AEs are coded and reported, please refer to the "Common Adverse Events" section later in this document).

## 4.3.5 Current Diseases (Other Than MS)

Diseases reported on the "General Medical History and Baseline Conditions Log" eCRF page are summarized as current diseases if disease status was recorded as "Ongoing" (with or without treatment) and disease end date was missing and the "End Date Unknown" box was not checked.

Diseases reported on the "Adverse Event/IRR/MS Relapse" eCRF page are summarized as current diseases a) AE onset date was on / after date of first ocrelizumab treatment in the main study and AE end date was either missing or on / after date of substudy randomization or b) if AE onset date was before date of substudy randomization, and AE intensity worsened after substudy randomization, and AE end date was unknown or on / after the date of substudy randomization.

Current diseases reported via the "General Medical History and Baseline Conditions Log" eCRF are summarized separately from those reported via the "Adverse Event/IRR/MS Relapse" eCRF page. In each of these two separate summaries, the total number of patients with at least one current disease and the total number of current diseases will be presented. The number and percentage of patients reporting current diseases will be presented by SOC and PT.

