## 4.3.7 Concomitant Treatments (Other Than For MS)

- Did patient receive any concomitant treatments, other than for MS? (defined as treatments with a start date on or after date of randomization, or with a start date before date of randomization but continuing into the substudy on/after date of randomization): number and percentage of patients (yes or no)
- Each previous non-MS treatment: number and percentage of patients receiving each treatment

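### SAP 4.3.4 and 4.3.5 have no place for a medical-history condition marked Ongoing whose recorded end date is on or after substudy randomization

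*SAP*

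**What the plan says.** SAP 4.3 presents baseline summaries by randomized group so that the comparability of the groups can be judged. Diseases other than MS are split into previous (4.3.4) and current (4.3.5), with separate rules for the General Medical History and Baseline Conditions Log and for the adverse-event page.

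For the medical-history log, an entry is previous in any of three cases:

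- (a) its status is Resolved;
- (b) its status is Ongoing "and disease end date was known to be before date of substudy randomization";
- (c) the End Date Unknown "box was checked (which indicates the disease had ended but the end date was unknown").

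An entry is current in one case only: its status is Ongoing ("with or without treatment) and disease end date was missing", with the End Date Unknown box left unchecked.

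Two neighbouring rules are drafted differently. For the adverse-event page, limb (a) of the current rule in 4.3.5 accepts an event whose "AE end date was either missing or on / after date of substudy randomization". For treatments, 4.3.7 counts as concomitant those that began on or after randomization, "or with a start date before date of randomization but continuing into the substudy on/after date of randomization".

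**The concern.** A baseline table should describe the patient at randomization. Under the log rules as written, the place of a condition that was active on that day depends on what happens to it later. If it is still open at the cut-off, it is current. If it has ended and the date has been entered, it is not.

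Two things follow. The current-disease counts are too low by however many such records exist. The same interim patients can also show fewer current diseases at the final analysis, because SAP section 1 says that final analyses other than the primary summary use all data up to the final cut-off. The adverse-event rule and the treatment rule both cover the parallel case, so the omission looks like an oversight and not a choice.

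**Working it through.** The plan gives no figure to reproduce here. The check is to run each type of log record through the two rules.

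| Row | Status | End date | End Date Unknown | 4.3.4 previous? | 4.3.5 current? | State at randomization |
|---|---|---|---|---|---|---|
| 1 | Ongoing | missing | unchecked | no | yes | active |
| 2 | Ongoing | before randomization | unchecked | yes | no | ended |
| 3 | Ongoing | on or after randomization | unchecked | **no** | **no** | active |
| 4 | Ongoing | missing | checked | yes | no | cannot be dated |
| 5 | Resolved | before randomization | unchecked | yes | no | ended |
| 6 | Resolved | on or after randomization | unchecked | **yes** | **no** | active |
| 7 | Resolved | missing | either | yes | no | cannot be dated |

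Row 3 is the gap: the record is in neither table. Row 6 is misplaced because limb (a) of 4.3.4 carries no date test. If the date test in limb (b) is read as governing Resolved as well, row 6 joins row 3 in neither table. On no reading does row 3 or row 6 reach the current table.

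**Can row 3 occur?** Protocol 5.3.5.9 puts on this log the conditions present at the main-study screening visit. SAP section 2 places randomization at Dose 2 or later. Limb (b) of 4.3.4 provides for Ongoing entries with an end date before randomization. For a condition present at screening, such a date has to be entered after screening. The SAP therefore expects end dates to be added to Ongoing entries, but it does not say how completely or for how long sites do so.

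**Illustrative size.** The documents give no resolution rate, so the rates below are assumptions. I also assume that follow-up is spread evenly from 0 to T years, that resolution has a constant rate h per year, and that every resolution is entered on the log. The share of active conditions affected by the cut-off is then

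1 − (1 − exp(−hT)) / (hT).

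SAP section 2 gives the first randomization of an already enrolled patient as 1 November 2018 and of a newly enrolled patient as 22 March 2019. SAP section 1 gives the interim cut-off as 27 September 2019. The longest follow-up is 330 days (47 weeks, T ≈ 0.90) for the first group and 189 days (27 weeks, T ≈ 0.52) for the second.

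| Assumed h per year | Newly enrolled, 0–27 weeks | Already enrolled, 0–47 weeks |
|---|---|---|
| 0.05 | 1.3% | 2.2% |
| 0.10 | 2.5% | 4.4% |
| 0.20 | 5.0% | 8.5% |
| 0.40 | 9.7% | 16.0% |

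Newly enrolled patients are the larger group: about 550 planned, against about 150 already enrolled. Incomplete recording would lower all of these shares. I give no figures for the final analysis because its cut-off date is not stated. Protocol Appendix 10, section 3.1, gives 14 February 2020 as the date when data had been cleaned, which is not a clinical cut-off.

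**The case against.** **The log may seldom be updated.** Protocol Appendix 1 schedules medical history at screening only, and Protocol 4.5.3 sends changes from baseline abnormalities to patient notes and new or worsened ones to the adverse-event page. A condition that resolves but is never re-entered stays Ongoing with no end date and is correctly counted as current. This stands as a limit on frequency. A reader might infer that every condition active at randomization and ended later is misplaced, but the documents support that only where the end has been recorded by the cut-off.

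**The Resolved route is conditional.** Limb (b) is needed only if an end date can be added while the status stays Ongoing, which suggests that status may be fixed at screening. In that case Resolved means resolved before randomization, and limb (a) needs no date test. This also stands: row 6 matters only if sites overwrite the status. Row 3 does not depend on it.

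**Comparability may be intact.** A reader might infer that the comparison of groups is biased. That would need resolution, or its recording, to differ by group. Both groups receive the same dose on the same schedule and differ only in infusion duration, under blinding, and nothing in the documents suggests a differential mechanism. The summaries of demography, MS history and pre-randomization IRRs do not use these rules.

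**The adverse-event page is not covered by this point.** Limb (a) of its current rule places events with onset on or after the first ocrelizumab dose and an end on or after randomization correctly. Limb (b) does depend on a later event ("AE intensity worsened after substudy randomization, and AE end date was unknown or on / after the date of substudy randomization"), but that is a separate drafting matter.

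**Conclusion.** Wrong as written, minor. The rules omit a clause, so an Ongoing log entry with an end date on or after randomization falls in neither baseline table. If status is also updated to Resolved, the condition is shown as previous. The conclusion that current-disease counts are too low, and can shrink between cut-offs, rests on sites adding end dates after randomization. Limb (b) of 4.3.4 makes that plausible but does not quantify it. The percentages above are illustrations under assumed rates and full recording, not estimates. The tables are descriptive and feed no model. No between-group bias is shown, and the primary IRR estimate is unaffected.

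**What to change.** Use one dated rule for the medical-history log.

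- **Current:** status Ongoing with the end date missing and End Date Unknown not checked; or any known end date on or after the date of substudy randomization, whatever the status.
- **Previous:** a known end date before randomization; or status Resolved with no end date available; or End Date Unknown checked.

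The unchecked-box condition must stay in the first limb of the current rule. Without it, an Ongoing entry with the box checked would meet both definitions. Placing undated ended conditions under previous should be stated as a convention, since they cannot be dated relative to randomization. A condition that ended after randomization on an unknown date would still be counted as previous.

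Applied to the seven rows above, the amended rules move rows 3 and 6 to current and leave the other five where they are. No row is then in both tables or in neither. The cost is one sentence each in SAP 4.3.4 and 4.3.5 and a small programming change, with no new data.

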## 4.3.6 Previous Treatments (Other Than For MS) Prior to Randomization

- Did patient receive any prior treatments, other than for MS? (defined as treatments with a stop date before date of randomization): number and percentage of patients (yes or no)
- Each previous non-MS treatment: number and percentage of patients receiving each treatment

## 4.3.7 Concomitant Treatments (Other Than For MS)

- Did patient receive any concomitant treatments, other than for MS? (defined as treatments with a start date on or after date of randomization, or with a start date before date of randomization but continuing into the substudy on/after date of randomization): number and percentage of patients (yes or no)
- Each previous non-MS treatment: number and percentage of patients receiving each treatment

## 4.4 EFFICACY ANALYSIS

No analyses of efficacy data are planned for this substudy.

## 4.5 SAFETY ANALYSES

This is a descriptive study and no formal inferential statistical analyses will be performed.

Summaries of the primary endpoint (proportion of patients with IRRs occurring during or within 24 hours after the 1st randomized infusion of ocrelizumab, as described below in Section 4.5.2.1) will provide point estimates of the between-treatment difference and associated symmetric two-sided 95% CIs. These summaries will be presented both unstratified and stratified for the stratification factors of 1st Randomized Dose and region (US / Canada / Australia vs. ROW).

Safety data include but are not restricted to AE data, laboratory data, previous and concomitant treatment data, infusion information including IRR data, withdrawal data, fatalities, vital signs and dosing information.

All summaries of IRRs will be based on the ITT Population (with the exception of additional sensitivity analyses for the primary endpoint only, based on PP and Safety Populations). All other safety summaries will be based on the Safety Population.

The term "Pre-Randomization" will be used refer to the period of time before the patient is randomized into the substudy. The term "Randomized Period" will be used to refer to the period of time during which a patient receives randomized treatment in the substudy. If a randomized patient discontinues from randomized treatment, they effectively discontinue from the substudy, and after this they will either:

- a) continue to receive ocrelizumab in the main study according to conventional infusion guidelines this period of time will be referred to as "Post Substudy, On Treatment"
- b) discontinue ocrelizumab treatment entirely and enter a safety follow-up period, as described in the main study protocol – this period of time will be referred to as "Post Substudy, Off Treatment"

## 4.5.1 Exposure to Study Medication

Within the substudy, in both randomized groups ocrelizumab is given as single infusions of 600mg at 24-week intervals. The only difference between the randomized groups is the duration of the infusion.

Patients will be considered to have received a dose of treatment if at least part of that infusion was given. If a dose is completely missed instead of delayed, the next dose number will be based on the number of previous doses received.

For each patient, the length of exposure to randomized treatment is from the date on which the patient first received randomized treatment (Substudy Day 1) until the last known alive date or CCOD, whichever is earlier. For patients who withdrew early from randomized treatment, the exposure is until the last known alive date (i.e., duration of exposure is equivalent to duration of observation period, and these terms are used interchangeably in this SAP). To summarize, the duration of exposure for a patient will be calculated as:

(Date of last contact\* – date of 1st Randomized Dose) + 1

\* Earlier of 1) date of CCOD 2) last known alive date

The following aspects of exposure to ocrelizumab will be summarized by randomized group:

- Treatment duration (weeks): frequency counts (number of patients and percentage) for 0-23 weeks, 24-47 weeks and 48-71 weeks will be presented
- Number of doses received: frequency counts (number of patients and percentage) and summary statistics (mean, SD and median) will be presented
- Total cumulative dose (derived to mg): summary statistics (mean, SD, median, lower and upper quartiles, minimum and maximum) will be presented

- Ocrelizumab infusion duration (minutes): summary statistics (mean, SD, median, lower and upper quartiles, minimum and maximum) will be presented by Randomized Dose and overall (all randomized doses).
- The number and percentage of infused patients with < 80% and ≥ 80% of the planned infusion volume will be presented, along with the number and percentage of infused patients who were pre-treated with methylprednisolone (or equivalent) only, with antihistamine only and with both methylprednisolone (or equivalent) and antihistamine. These summaries will be presented by Randomized Dose and then by Dose within Randomized Dose (and overall within Randomized Dose i.e. across all Doses).

- The number and percentage of patients in either randomized group with any IRR receiving <80% or ≥80% of the planned ocrelizumab volume will be presented, along with the number and percentage of infused patients in the shorter infusion group with any IRR receiving <80% or ≥80% of the planned saline volume. These summaries will be presented by Randomized Dose and then by Dose within Randomized Dose (and overall within Randomized Dose i.e. across all Doses).

## 4.5.2 Adverse Events

## 4.5.2.1 Infusion-Related Reactions

IRRs are collected on the "Adverse event/IRR/MS relapse" and "Infusion Related Reaction" eCRF pages. The symptom(s) of an IRR and the IRR itself may be of different intensities. IRR symptoms (collected on the "Infusion Related Reaction" eCRF page) will be coded in MedDRA and summarized by SOC and PT. IRRs (in fact all AEs) are categorized on the "Adverse Event/IRR/MS Relapse" eCRF page as occurring 1) during infusion or 2) within 24 hours after end of infusion.

Summaries of pre-randomization IRRs and serious IRRs are described above in Section 4.3.3. In all other summaries of IRRs, only IRRs occurring during the substudy will be included. IRRs occurring after withdrawal from the substudy will not be included in these IRR summaries (but will be included in AE summaries, which will include all AEs with an onset date after the date of randomization, even if the onset is after the patient discontinues randomized treatment).

The primary endpoint of this substudy is the proportion of patients with IRRs occurring during or within 24 hours after the 1st randomized infusion of ocrelizumab. A stratified method will be applied, to take account of the two stratification factors, region and 1st Randomized Dose. The weighted average of the proportion difference across strata based on Cochran-Mantel-Haenszel weights is estimated. This approach will result in a stratified estimated difference between the proportions in the two randomized groups, which will be presented along with an associated 95% CI. This method is described by (Zhao et al. 2001) and its practical implementation is further described by (Zhang 2016). The (unstratified) estimated difference between the proportions in the two randomized by (Zhang 2016).

groups will also be presented along with an associated 95% CI. This summary will be presented for all patients, for patients with at least one pre-randomization IRR and for patients with no pre-randomization IRRs. The primary endpoint will be summarized for the ITT Population, and also for the PP and Safety Populations additionally, as sensitivity analyses. The primary endpoint will be further described in graphical barchart format (ITT Population only).

If the IA leads to an early unblinding of the substudy team to patients included in the IA, in order to eliminate potential bias from any data changes which might arise after the IA, data used for the primary summary (IRRs at 1st Randomized Dose) in the IA population (N=400 approximately) locked at the IA CCOD will be combined with those in the post-IA population (N=250 to 300 approximately) locked at the final CCOD to perform the primary summary at the final analysis. Final analyses other than the primary summary will be performed on all data up to the final CCOD.

An IRR overview summary will be presented, showing the number and percentage of infused patients with any IRR and any serious IRR. This summary will be presented by Randomized Dose and then by Dose within Randomized Dose (and overall within Randomized Dose i.e. across all Doses), and overall (all randomized doses). This summary will be presented for all patients, for patients with at least one pre-randomization IRR and for patients with no pre-randomization IRRs.

Further summaries of IRRs will be presented by Randomized Dose and then by Dose within Randomized Dose as follows:

- The number and percentage of patients with IRR symptoms will be presented by SOC (in decreasing order of overall incidence) and PT (in decreasing order of overall incidence).
- The number and percentage of patients with IRRs by most extreme intensity will be presented (Grade 1 = mild, Grade 2 = moderate, Grade 3 = severe, Grade 4 = life-threatening, grade 5 = fatal). Multiple IRRs in one patient are counted only once at the most extreme (highest) intensity observed.
- The number and percentage of patients with IRRs, grouped by most extreme intensity into not severe (Grade 1 or 2) and severe (Grade 3 to 5) will be presented. Again, multiple IRRs in one patient are counted only once at the most extreme (highest) intensity observed.
- The number and percentage of patients with IRRs leading to intervention in ocrelizumab infusion, with intervention defined as infusion slowed down, or infusion interrupted or infusion discontinued
- The number and percentage of patients with IRR symptoms leading to discontinuation of ocrelizumab infusion will be presented by SOC (in decreasing order of overall incidence) and PT (in decreasing order of overall incidence).

- The number and percentage of patients with IRR symptoms leading to interruption of ocrelizumab infusion will be presented by SOC (in decreasing order of overall incidence) and PT (in decreasing order of overall incidence).
- The number and percentage of patients with IRR symptoms leading to slowing down of ocrelizumab infusion will be presented by SOC (in decreasing order of overall incidence) and PT (in decreasing order of overall incidence).
- The number and percentage of patients with IRRs who received pre-medications (methylprednisolone (or equivalent) only, antihistamine only, methylprednisolone (or equivalent) plus antihistamine)
- The number and percentage of patients with IRR symptoms will be presented by SOC (in decreasing order of overall incidence) and PT (in decreasing order of overall incidence), shown separately for the following two time periods: a) during ocrelizumab/saline infusion and b) within 24 hours after the end of ocrelizumab/saline infusion
- The number and percentage of patients with IRR symptoms will be presented by SOC (in decreasing order of overall incidence) and PT (in decreasing order of overall incidence), shown separately for the following two time periods: a) from the start of ocrelizumab infusion to switch/dummy switch to saline infusion and b) from switch/dummy switch to saline infusion.
- The number and percentage of patients with IRRs by outcome (recovered / resolved, recovered / resolved with sequelae, recovering / resolving, not recovered / not resolved, fatal and unknown)
- The number and percentage of patients with IRRs who received symptomatic treatments for any IRR

All IRRs and symptoms occurring before and during the substudy will be listed, with separate listings created for IRRs occurring prior to randomization and for IRRs occurring post-randomization during the substudy.

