1. BACKGROUND

1.1 RATIONALE FOR THE SUBSTUDY

Ocrelizumab is administered by intravenous infusion as a 600 mg dose every 6 months. The first ocrelizumab dose of 600 mg is always administered as a divided dose (2 x 300 mg infusions administered 14 days apart) to help reduce the incidence of infusion-related reactions (IRRs) which is highest upon the first infusion of ocrelizumab. The incidence and severity of IRRs is also higher upon the first infusion of all other B-cell depleting agents. The subsequent doses of ocrelizumab are administered as a single 600 mg infusion, with a minimum interval of 5 months to be maintained between each dose of ocrelizumab.

IRRs are among the most frequent adverse events associated with ocrelizumab treatment. During the Phase III relapsing multiple sclerosis (RMS) controlled treatment period, the incidence of IRRs in patients receiving ocrelizumab was highest during the first infusion (Dose 1, Infusion 1; 27.5% of RMS OPERA I and II [WA21092 and WA21093] patients pooled), and with subsequent dosing IRRs occurred with decreasing incidence. After the first dose, the incidence (RMS OPERA I and II pooled: 4.7% to 13.7% of patients), severity (Grade 1 or 2; RMS OPERA I and II pooled: 92.6% of patients) and symptoms (in >= 10% of RMS patients with IRRs: pruritus, rash, throat irritation and flushing) of IRRs were similar in both studies.

A preliminary analysis was performed on an ad-hoc data cut (06-April-2018) in the main study (ENSEMBLE) including 675 patients who had received the first infusion of dose 1 and 172 who had received dose 2 at week 24. The proportions of patients with IRRs were 28.7% and 12.2% at dose 1 and dose 2, respectively, which were similar to the rates of 27.5% and 13.5% observed in OPERA I and II pooled.

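### The all-patient IRR risk difference is adjusted for region and 1st Randomized Dose but not for pre-randomization IRR history, so its 95% CI is probably somewhat wider than necessary

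*SAP*

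**What the plan says.** SAP 4.5.2.1 defines the endpoint: "The primary endpoint of this substudy is the proportion of patients with IRRs occurring during or within 24 hours after the 1st randomized infusion". For the comparison it states "A stratified method will be applied, to take account of the two stratification factors", these being region and 1st Randomized Dose, and then "The weighted average of the proportion difference across strata based on Cochran-Mantel-Haenszel weights is estimated". An unstratified difference with its own 95% CI is also given. SAP 4.5 asks for both versions, with "associated symmetric two-sided 95% CIs", and does not say which is the main result. Protocol Appendix 10, section 6.5, lists the plain difference first and the stratified analysis as an addition.

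IRR history appears in two other roles. SAP 4.3.3 tabulates pre-randomization IRRs as a baseline characteristic. SAP 4.5.2.1 repeats the primary summary "for patients with at least one pre-randomization IRR and for patients with no pre-randomization IRRs". It is not a stratum in either all-patient estimate.

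The variable should be complete. SAP Section 2 says the shorter infusion is never given at Dose 1. New patients are randomized at Dose 2 and previously enrolled patients at Dose 3, 4 or 5, so everyone has been infused before randomization.

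**The concern.** The substudy has no hypothesis test and no margin. SAP 2.3 judges its sample sizes, including the interim at about 400 patients, by the width of the CI for this one difference. A baseline variable that predicts the outcome narrows that interval at no cost in data and leaves the target a risk difference. The sponsor evidently regards IRR history as relevant, since it pre-specifies subgroups on it.

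Randomization is stratified by region and dose, so IRR history is balanced only on average. The baseline table and the subgroup split would show an imbalance, but no planned all-patient estimate adjusts for it.

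**Working it through.** **Plan's own figures.** SAP Tables 2 and 3 reproduce as unstratified Wald intervals, half-width = 1.96 × √[p1(1−p1)/n + p2(1−p2)/n].
- N=650 (325 per arm), 12.4% in both arms: 1.96 × √(2 × 0.124 × 0.876 / 325) = 5.07 points; the SAP gives 5.1.
- N=400 (200 per arm): 1.96 × √(2 × 0.124 × 0.876 / 200) = 6.46 points; the SAP gives 6.5.
- All seven rows of each table agree to 0.1 point.
- Pooled rate: (500 × 13.7 + 40 × 9.6 + 110 × 7.8) / 650 = 12.45%; the SAP gives 12.4%.

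**What stratifying by dose recovers.** With the dose-specific rates in SAP 2.3, stratifying by dose moves the half-width only from 5.08 to 5.06.

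**Inputs for IRR history.**
- Prevalence π = 28.7%, from Protocol Appendix 10, section 1.1: "The proportions of patients with IRRs were 28.7% and 12.2% at dose 1 and dose 2". This is the Dose 1 rate in main-study patients. It is a proxy for any pre-randomization IRR among randomized patients: those randomized at Dose 3 to 5 had more infusions at which to react, and a prior serious IRR is an exclusion.
- Risk ratio (RR) of an IRR at the first randomized dose, prior IRR versus none: not in the documents. Assumed range 1 to 5.

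**Formula.** With overall rate P, rate without history pB = P / (1 + π(RR − 1)) and rate with history pA = RR × pB, adjustment multiplies the variance by 1 − r, where r = π(1−π)(pA − pB)² / [P(1−P)].

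Example at P = 12.4%, RR 3: pB = 0.124 / 1.574 = 0.0788, pA = 0.2363, r = 0.287 × 0.713 × 0.1576² / (0.124 × 0.876) = 0.047. Half-width = 5.07 × √0.953 = 4.95.

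| Setting | Unadjusted | RR 1 | RR 2 | RR 3 | RR 5 |
|---|---|---|---|---|---|
| P = 12.4%, N = 650 | 5.07 | 5.07 | 5.02 | 4.95 | 4.81 |
| P = 12.4%, N = 400 | 6.46 | 6.46 | 6.40 | 6.31 | 6.13 |
| P = 23.5%, N = 580 | 6.90 | 6.90 | 6.77 | 6.54 | 6.10 |

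The last row uses roughly the rates reported in Protocol 1.2 (67 and 71 patients with IRRs among 291 and 289 randomized). The exact pooled rate is 138/580 = 23.8%, which changes the unadjusted half-width only to 6.93.

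**Chance imbalance.** At N=650 the between-arm difference in prior-IRR prevalence has SD √(2 × 0.287 × 0.713 / 325) = 3.55 points. At RR 3 and P = 12.4%, a 2-SD imbalance would shift the crude difference by 2 × 3.55 × 0.1576 = 1.1 points.

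**Simulation** (2,000 trials per scenario, N=650, 12.4% rate, 30% in one region assumed). Mean CI half-widths:

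| RR | Region × dose | Region × dose × history | Two-level dose × history (no region) |
|---|---|---|---|
| 1 | 5.01 | 5.00 | 5.04 |
| 2 | 5.01 | 4.93 | 4.99 |
| 3 | 5.02 | 4.84 | 4.92 |
| 5 | 5.00 | 4.66 | 4.75 |

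Coverage of these intervals stayed between 94.7% and 96.1%. Part of the narrowing in the full cross is an artefact of sparse strata: at RR 1 the actual spread (1.96 × empirical SD) was 5.06 without history and 5.11 with it.

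**Stratum sizes.** The full cross has 2 × 4 × 2 = 16 strata. With about 40 patients at Dose 3, 28.7% with a prior IRR and 30% in the smaller region, one stratum would expect 40 × 0.287 × 0.30 ≈ 3 patients over both arms. Collapsing to Dose 2 versus Dose 3 or later leaves 8 strata; the corresponding one expects 150 × 0.287 × 0.30 ≈ 13.

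**The case against.** The plan can be defended on several grounds. Analysing by the randomization strata is standard. At the planning rate the gain is 0.05 to 0.26 point for RR 2 to 5 and nil at RR 1, and no margin or test depends on it. The sponsor accepted a far larger loss, from 5.1 to 6.5 points, in moving from 650 to 400 patients. The baseline table would reveal an imbalance, and a reader could combine the two subgroup results. The higher rate was not available to the SAP, which was written around 12.4%. Appendix 10 also reports that the interim became the primary analysis and that the substudy has been unblinded.

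Most of this stands and limits the point. It does not remove it: the subgroup split gives no adjusted overall estimate with its own CI, and the variable is already collected. The timing affects how an added analysis must be labelled, not whether the SAP text could have been better.

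A reader might infer that the main CI is demonstrably too wide, or that the comparison is biased. The documents support neither. They give no IRR rate by history, do not name the stratified CI as the main one, and contain nothing that undermines randomization or coverage. Nor should the 23.8% rate be paired with N=650 to claim a saving: that rate comes from 580 unblinded patients.

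**Conclusion.** The point holds as a conditional one about efficiency. Both all-patient estimates omit a complete, already tabulated baseline variable, so the 95% CI is probably somewhat wider than it need be, and a chance imbalance in IRR history would be shown but not adjusted for.

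For RR 1 to 5, the interval would be 0% to about 5% narrower at the planning rate with N=650, and 0% to about 12% narrower at about 23.5% with N=580. These ranges rest on an assumed risk ratio and on 28.7% as a proxy prevalence. They do not show that the conclusion about the shorter infusion would change. A related gap is that neither the SAP nor the protocol says which all-patient estimate is the main one.

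**What to change.** In SAP 4.5.2.1, pre-specify a Cochran-Mantel-Haenszel weighted risk difference stratified by region, dose (Dose 2 versus Dose 3 or later) and any pre-randomization IRR (yes/no). Fix the dose collapse in advance; do not let it depend on which cells turn out empty. Keep the region-by-dose and unstratified estimates alongside, and state which of the three is the main estimate. If the analysis is added after unblinding, label it supportive and post hoc.

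The cost is a short addition to the SAP text and one derived stratum variable, with no new data. The downsides are a few small strata, more noticeable at N=400, and no gain if IRR history is not prognostic.
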